## **8.4 Safety and Tolerability**

Safety assessments are specified within the section below. The methods for recording the assessments are specified in the Site Operations Manual. The Assessment Schedule ([Table 8-1](#)) details the timing of when each assessment is to be performed.

For details on AE collection and reporting, refer to AE section ([Section 10.1.1](#)).

### **8.4.1 Physical examination**

Information for all physical examinations must be included in the source documentation. Clinically relevant findings that are present prior to signing informed consent must be recorded on the appropriate CRF that captures medical history. Significant findings made after signing informed consent which meet the definition of an Adverse Event must be recorded as an adverse event. See the SOM for details.

### **8.4.2 Vital signs**

Vital signs include BP and pulse measurements. See the SOM for details.

### 8.4.3 Laboratory evaluations

A central laboratory will be used for analysis of all safety specimens collected, and will also be used for a repository for select bio samples.

Details on the collections, shipment of samples and reporting of results by the central laboratory are provided to investigators in the laboratory manual. Repository samples may be shipped to a Novartis analysis laboratory or contracted analysis laboratory at any time during the study for processing and analysis.

Clinically notable laboratory findings are defined in [Appendix 1](#) and the Laboratory Manual. Clinically significant abnormalities must be recorded on the relevant section of the medical history/Current medical conditions/AE CRF/ e(CRF) page as appropriate. Clinically relevant deviations of laboratory test results occurring during or at completion of the study must be reported and discussed with Novartis personnel. The results should be evaluated for criteria defining an adverse event and reported as such if the criteria are met. Repeated evaluations are mandatory until normalization of the result(s) or until the change is no longer clinically relevant. In case of doubt, Novartis personnel should again be contacted.

#### 8.4.3.1 Hematology

Hemoglobin, hematocrit, red blood cell count, white blood cell count with differential and platelet count will be measured. A coagulation panel including PT/INR, aPTT, and fibrinogen will be measured.

#### 8.4.3.2 Clinical chemistry

Sodium, potassium, creatinine, BUN/urea, uric acid, chloride, albumin, calcium, phosphate, bicarbonate/HCO3, LDH, amylase, lipase, creatine kinase (CK), glucose

#### 8.4.3.3 Liver function tests

Alanine aminotransferase (ALT), aspartate aminotransferase (AST), total bilirubin (TBL), serum albumin (Alb), prothrombin time (PT)/ international normalized ratio (INR), alkaline phosphatase (ALP), gamma-glutamyl transferase (γGT)

#### 8.4.3.4 Urinalysis and renal function

Dipstick/macroanalysis measurements for specific gravity, protein, glucose and blood will be performed. Microscopy, WBC, RBC and sediments will also be assessed in case of an abnormal dipstick test.

The following assessments for renal function will also be completed:

- Urine albumin-creatinine ratio (UACR) at serial time points, as specified in the [Assessment Schedule](#)
- 24-hour urinary collection at baseline and end of study, measured for albumin
- Estimated glomerular filtration rate (eGFR), as determined by the Chronic Kidney Disease Epidemiology Collaboration (CKD-EPI) equation ([Levey and Stevens 2010](#)).
- Free water clearance

#### **8.4.3.5 Type 2 diabetes and glycemc control**

- HbA1c
- Fasting lipid profile (total cholesterol, HDL-C, LDL-C, triglycerides and Lp(a))

#### **8.4.4 Electrocardiogram (ECG)**

Triplicate twelve-lead ECGs will be collected at the time-points specified in the [Schedule of Assessments](#). At each time point, three serial 12-lead ECGs, at 5 minute intervals, will be recorded. Full details of all procedures relating to the triplicate ECG collection and reporting are contained in the ECG technical manual and SOM.

- PR interval, QRS duration, heart rate, RR, QT, QTc will be assessed
- The Fridericia QT correction formula (QTcF) (calculated with the RR interval expressed in seconds) should be used for clinical decisions
- If clinically significant abnormalities are identified that were present prior to the informed consent signature, then it should be recorded on the relevant medical history CRF page.
- After informed consent signature, any clinically significant abnormalities are recorded on the Adverse Events page thereafter.
  - Clinically significant findings MUST be recorded on the AE CRF and should be discussed with the sponsor in a timely fashion.

#### **8.4.5 Pregnancy and assessments of fertility**

All pre-menopausal women who are not surgically sterile will have pregnancy testing performed at selected time points during the study. See the Assessment Schedule, [Table 8-1](#), for timing of the protocol required pregnancy testing.

Additional pregnancy testing may be performed to meet local requirements. A positive pregnancy test requires immediate interruption of study treatment until serum  $\beta$ -hCG is performed and found to be negative.

If positive, the patient will enter the post-treatment follow up period (see [Section 10.1.4](#)).

If additional pregnancy testing is needed per local requirements, those additional results will be kept as source documentation only.

#### **8.4.6 Appropriateness of safety measurements**

Planned safety assessments are based upon expected organ toxicity as discussed in the rationale of study design ([Section 4.1](#)) and risk-benefit sections ([Section 4.5](#)).

### **8.5 Additional assessments**

#### **8.5.1 Clinical Outcome Assessment - Visual Analog Scale (VAS)**

The participant must be given the PRO measure(s) to be completed at the scheduled visit before any clinical assessments are conducted. Participant's refusal to complete all or any part of a PRO measure should be documented in the study data capture system and should not be captured as a protocol deviation. Handling of protocol deviations can be modified if needed.

Participant questionnaires should be completed in the language most familiar to the participant.

The participant should be given sufficient space and time to complete the PRO measure(s).

The site personnel or delegate should check PRO measure(s) for completeness and ask the participant to complete any missing responses. The responses stored electronically in the database will be considered the source file.

Completed measure(s) (including when using paper PRO measures and any unsolicited comments written by the participant) must be reviewed and assessed by the investigator for responses which may indicate potential AEs or SAEs before any clinical study examinations are performed. This assessment should be documented in study source records. If AE or SAE are confirmed, the study investigator should not encourage the participant to change responses reported in the completed questionnaires. Study investigators must follow reporting instructions outlined in [Section 10.1.1](#) of the study protocol.

A 10 cm visual analogue scale (VAS) will be used to assess the severity of patients itch (ranging from 0 = no itch at all, to 10 = the worst itch imaginable itch). The score (distance from left) on the VAS will be recorded by the patient by marking with a line and used to test for an effect of nifedexor over placebo. The scale will be completed by patients as indicated in [Table 8-1](#) (Assessment schedule).

### **8.5.2 Pharmacokinetics**

PK samples will be collected at the time points defined in the Assessment schedule, [Table 8-1](#). Follow instructions outlined in the central laboratory manual and SOM regarding sample collection, numbering, processing and shipment. See [Section 8.5.3.2](#) regarding the potential use of residual samples.

Commercially Confidential Information

Commercially Confidential Information

Commercially Confidential Information

## 9 Study discontinuation and completion

### 9.1 Discontinuation

#### 9.1.1 Discontinuation of study treatment

Discontinuation of study treatment for a patient occurs when study treatment is stopped earlier than the protocol planned duration and can be initiated by either the patient or the investigator.

The investigator must discontinue study treatment for a given patient if he/she believes that continuation would negatively impact the patient's well-being.

**Study treatment MUST be discontinued under the following circumstances:**

- Hypersensitivity (CTCAE grade 2 or higher, CTCAE Version 5.0) reaction to nidufexor.
- Adverse events, abnormal laboratory values or abnormal test result that indicate a safety risk to the patient, in the opinion of the investigator
- An adverse event that is a CTCAE Grade 3 CTCAE Version 5.0 and believed to be related to the study drug (apart from liver and renal events - see below).
- A liver safety event with ALT, AST, total bilirubin and/or alkaline phosphatase elevations mandating study treatment discontinuation. Please refer to [Section 10.2.1](#) (Liver safety monitoring), [Table 16-1](#) and [Table 16-2](#) for further instructions and monitoring.

- A renal safety event with serum creatinine elevations mandating study treatment discontinuation. Please refer to [Section 16.3](#) and [Table 16-3](#) for further instructions and monitoring.
- Pregnancy (see [Section 10.1.4](#))
- Any protocol deviation that results in a significant risk to the patient's safety, in the opinion of the investigator.
- Following emergency unblinding

If a patient presents with COVID-19 symptoms, this does not require the patient to be discontinued. Please refer to [Section 6.5](#) for further instructions.

If discontinuation of study treatment occurs, the investigator must determine the primary reason for the patient's premature discontinuation of study treatment and record this information on the applicable CRF.

Patients who discontinue study treatment or who decide they do not wish to participate in the study further should NOT be considered withdrawn from the study UNLESS they withdraw their consent ([Section 9.1.2](#)). Where possible, they should be scheduled for a visit as soon as possible, at which time all of the assessments listed for the final visit should be performed, with top priority for assessments as noted in the [Assessment Schedule](#) for the EOS visit. At this final visit, all dispensed investigational product must be collected, and reconciled.

If they fail to complete these assessments for unknown reasons, every effort (e.g. telephone, e-mail, letter) should be made to contact the patient/pre-designated contact as in [Section 9.1.3](#) (Lost to follow-up). This contact preferably should be done according to the study visit schedule.

After study treatment discontinuation, the following data (at a minimum) should be collected at abbreviated study visits or via telephone/email contact:

- new / concomitant treatments
- adverse events/Serious Adverse Events

The investigator must also contact the IRT to register the patient's discontinuation from study treatment.

If discontinuation occurs because treatment code has been broken, please refer to emergency breaking of treatment code, [Section 6.6.3](#).

All patients that complete the study should have a post study safety follow-up phone call conducted approximately 28 days after last dose. In the event of premature discontinuation from the study, the study staff should attempt a post study safety follow-up phone call approximately 28 days after the patient's last visit. In the event of withdrawal of consent, the study staff should follow the guidance in [Section 9.1.2](#). The information collected is kept as source documentation. All SAEs reported during this time must be reported as described in [Section 10.1.3](#).

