### **10.2.2 Renal safety monitoring**

Once a participant has been exposed to study treatment, the following two categories of abnormal renal laboratory alert values should be assessed during the study period:

Serum creatinine increase  $\geq 25\%$  compared to baseline during normal hydration status. Baseline serum creatinine is determined as the mean of two serum creatinine measurements (e.g. at screening and pretreatment).

- Albumin-creatinine ratio (UACR) increase  $\geq 2X$  baseline

Abnormal renal event findings must be confirmed within 24-48 hours after the first assessment.

Once a participant is exposed to study treatment, renal laboratory alerts or renal safety events should be monitored and followed up by the investigator or designated trial staff as summarized in [Table 16-3](#).

Every renal laboratory trigger or renal event as defined in [Table 16-3](#) should be followed up by the investigator or designated personnel as summarized in [Section 16.3](#).

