**Table 16-2 Follow Up Requirements for Liver Events and Laboratory Triggers**

Criteria	Actions required	Follow-up monitoring
Potential Hy's Law case a	
 
Discontinue the study treatment immediately
 
Hospitalize, if clinically appropriate
 
Establish causality
 
Complete liver CRF
 
	ALT, AST, TBL, Alb, PT/INR, ALP and $\gamma$ -GT until resolution c (frequency at investigator discretion)
ALT or AST		
for patients with normal baseline: $> 8 \times$ ULN For patients with elevated baseline $> 8 \times$ ULN or $> 500$ U/L whichever comes first	
 
Discontinue the study treatment immediately
 
Hospitalize if clinically appropriate
 
Establish causality
 
Complete liver CRF
 
	ALT, AST, TBL, Alb, PT/INR, ALP and $\gamma$ GT until resolution c (frequency at investigator discretion)
For patients with normal baseline: $> 5$ to $\leq 8 \times$ ULN For patients with elevated baseline: $>5$ to $\leq 8 \times$ ULN or $>5X$ ULN to $\leq 500$ U/L whichever comes first	
 
Repeat LFT within 48 hours
 
If elevation persists, continue follow-up monitoring
 
If elevation persists for more than 2 weeks, discontinue the study drug
 
Establish causality
 
Complete liver CRF
 
	ALT, AST, TBL, Alb, PT/INR, ALP and $\gamma$ GT until resolution c (frequency at investigator discretion)
$> 3 \times$ ULN accompanied by symptoms b	
 
Discontinue the study treatment immediately
 
Hospitalize if clinically appropriate
 
Establish causality
 
Complete liver CRF
 
	ALT, AST, TBL, Alb, PT/INR, ALP and $\gamma$ GT until resolution c (frequency at investigator discretion)
$> 3$ to $\leq 5 \times$ ULN (patient is asymptomatic)	
 
Repeat LFT within the next week
 
If elevation is confirmed, initiate close observation of the patient
 
	Investigator discretion Monitor LFT within 1 to 4 weeks
ALP (isolated)		

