### 16.3 Appendix 3: Specific Renal Alert Criteria and Actions and Event Follow-up

**Table 16-3 Specific Renal Alert Criteria and Actions**

Serum Event	
Serum creatinine increase 25 – 49% compared to baseline	Confirm 25% increase after 24-48h Follow up within 2-5 days
Acute Kidney Injury: Serum creatinine increase 50% compared to baseline	Follow up within 24-48h if possible Consider study treatment interruption Consider patient hospitalization /specialized treatment
Urine Event	
Albumin-creatinine ratio increase $\geq 2$ fold from baseline value	Confirm value after 24-48h Perform urine microscopy Consider study treatment interruption / or discontinuation
	Blood glucose (fasting) Perform serum creatinine, UACR
New dipstick hematuria $\geq 1+$ not due to trauma	Urine sediment microscopy Perform serum creatinine, UACR
For all renal events:	
Document contributing factors in the CRF: co-medication, other co-morbid conditions, and additional diagnostic procedures performed	
Monitor patient regularly (frequency at investigator's discretion) until either:	
Event resolution: sCr within 10% of baseline or albumin-creatinine ratio within 50% of baseline, or	
Event stabilization: sCr level with $\pm 10\%$ variability over last 6 months or albumin-creatinine ratio stabilization at a new level with $\pm 50\%$ variability over last 6 months.	

[Bakris et al 2015](#), [de Zeeuw et al 2014](#)

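### The mandatory creatinine stop in Protocol 9.1.1 points to a table with no creatinine stop, while renal events are exempt from the related Grade 3 stop

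*Protocol*

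**What the plan says.** Protocol 9.1.1 has a list of circumstances in which study treatment must be discontinued. Three entries matter here.

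- **Grade 3 rule.** A CTCAE Grade 3 event stops treatment if it is "believed to be related to the study drug (apart from liver and renal events - see below").
- **Liver bullet.** "A liver safety event with ALT, AST, total bilirubin and/or alkaline phosphatase elevations mandating study treatment discontinuation", with a pointer to Section 10.2.1 and Tables 16-1 and 16-2.
- **Renal bullet.** "A renal safety event with serum creatinine elevations mandating study treatment discontinuation", with a pointer to Section 16.3 and Table 16-3.

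Table 16-3 has two creatinine rows. For a 25-49% rise from baseline the action is "Confirm 25% increase after 24-48h Follow up within 2-5 days". For a 50% rise, labelled acute kidney injury, it is "Follow up within 24-48h if possible Consider study treatment interruption Consider patient hospitalization" or specialized treatment.

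Section 10.2.2 sets the alert at a creatinine rise of at least 25% and asks for confirmation. It then says that "renal laboratory alerts or renal safety events should be monitored and followed up by the investigator or designated trial staff", again by reference to Table 16-3.

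**The concern.** A mandatory stopping rule needs a condition that a site can recognise. The renal bullet describes its condition only as a creatinine rise that mandates stopping, and the table it cites names no such rise.

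The exemption makes this more than loose wording. Without it, a related Grade 3 renal event would stop treatment under the general rule. With it, the event is passed to a bullet that nothing in the cited text can trigger.

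The trial enrolls patients with UACR of at least 300 mg/g on an ACEI or ARB, and with eGFR as low as 30 mL/min/1.73 m², so creatinine is a central safety signal. Two sites could handle the same related Grade 3 creatinine rise differently, one stopping and one continuing, and a monitor could not tell from this bullet which had departed from the protocol.

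**Working it through.** The plan gives no figure to reproduce here, and the point rests on no power, standard deviation or sample size. The check follows each pointer to its end.

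1. **Renal bullet to Table 16-3.** Creatinine rows: 2. Rows requiring discontinuation: 0. The 25-49% row asks for confirmation and follow-up. The 50% row asks for follow-up, and asks the investigator to consider interruption and hospitalization.
2. **Rest of Table 16-3.** Discontinuation is named only in the row for a UACR rise of 2-fold or more, as something to consider. The hematuria row, and a urine row whose trigger cell is blank in the text available, list tests only. No row of any kind requires a stop.
3. **Section 10.2.2.** It sets alert levels and a 24-48 hour confirmation, then refers back to Table 16-3. No stop level is added.
4. **Grade 3 rule.** A related Grade 3 event that is neither hepatic nor renal stops treatment. A related Grade 3 renal event is exempt and goes to the renal bullet, which by steps 1 to 3 has no qualifying level.
5. **Liver comparison.** Table 16-2 has 10 rows.
   - Four require an immediate stop ("Discontinue the study treatment immediately"): potential Hy's Law case, ALT/AST above 8 × ULN (or above 500 U/L with elevated baseline), ALT/AST above 3 × ULN with symptoms, and jaundice.
   - Two require a stop if the elevation persists: ALT/AST above 5 and up to 8 × ULN for more than 2 weeks, and total bilirubin above 2 × ULN on repeat.
   - So 4 + 2 = 6 of 10. The isolated alkaline phosphatase row has no stop, although the liver bullet names that analyte. The liver bullet therefore resolves for ALT/AST and total bilirubin only.
6. **What still applies to a renal event.**
   - Section 9.1.1, opening text: "The investigator must discontinue study treatment for a given patient if he/she believes that continuation would negatively impact" the patient.
   - Section 9.1.1, the bullet on events or laboratory values that the investigator judges a safety risk. It sits on the mandatory list.
   - Section 6.5: discretion to discontinue after extended interruptions related to adverse events.
   - Section 9.1.4: an enrollment hold and safety review after two related SAEs, or three patients with a similar related event of Grade 3 or higher. It has no renal exemption.
   - Table 16-3: confirmation, follow-up, documentation of contributing factors, and monitoring to resolution or stabilization.

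The patient-level stops in step 6 depend on the investigator's judgement. Section 9.1.4 acts on the study. None supplies a creatinine level at which one patient must stop.

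**The case against.** The strongest reply is that the bullet cites Table 16-3 for instructions and monitoring, not as the source of a threshold, and that the stop is meant to be the investigator's call. The judgement stops are themselves mandatory once a risk is perceived, and whether to set a numeric creatinine limit is the sponsor's choice. All of that is fair. It does not rescue the text. If judgement is the intended rule, the renal bullet repeats the safety-risk bullet, the word mandating is wrong, and the exemption only takes away the Grade 3 stop.

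A second reply is that the liver bullet has a similar flaw for isolated alkaline phosphatase, which suggests template wording. That stands as far as it goes. But most of the liver bullet leads to real stops, and none of the renal bullet does.

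A third is that text may be missing. One urine trigger cell is blank and part of Section 6.5 is absent, but both creatinine rows read complete and Section 10.2.2 shows no redaction. The Site Operations Manual is not available here, but the bullet does not cite it.

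A reader might infer that patients with acute kidney injury have no stopping protection, or that site conduct cannot be audited. The documents support neither. The routes in step 6 of the working remain, Table 16-3 sets timed duties that can be checked, and the main reason for any discontinuation must be recorded.

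**Conclusion.** The point holds in a limited form. No creatinine row (0 of 2) triggers the renal bullet, Section 10.2.2 does not fill the gap, and the Grade 3 exemption removes related renal events from a rule that would otherwise apply. What is missing is an objective mandatory stop for a related Grade 3 renal event, not every means of stopping.

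Severity is minor to should-fix: it is a drafting inconsistency in a mandatory safety rule, softened by the remaining safeguards and cheap to correct. This rests on Sections 6.5, 9.1.1, 9.1.4 and 10.2.2 and Tables 16-2 and 16-3 as shown. The documents give no expected number of renal events, so no frequency is claimed.

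**What to change.** By amendment, delete the words *and renal* from the exemption in the Grade 3 rule, so that related Grade 3 renal events stop treatment. Then choose one:

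- **(a)** Remove the renal bullet from the mandatory list and leave the *consider* actions in Table 16-3. Rewording the bullet to *consider* where it stands would contradict the heading above it.
- **(b)** Keep the bullet and add to Table 16-3 a confirmed creatinine rise, chosen by the sponsor, that requires discontinuation. The documents suggest no value.

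Only (b) gives an objective creatinine level. Under (a) the stop still depends on the judgement of relatedness, and these documents do not state which creatinine rise counts as Grade 3.

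**Cost.** Amendment wording, a site notice and a few more early stops. SAP 2.2 drops end-of-study assessments made before Day 135 or more than 10 days after the last dose. With visit day V and last dose day L, keeping the value needs V ≥ 135 and V − L ≤ 10, so L ≥ 135 − 10 = 125. A last dose on or before Day 124 therefore loses the Week 24 value in the PD-set analysis. From Day 125 to 134, it survives only if the visit falls on Day 135 or later and within those 10 days. The UACR model still uses the patient's earlier visits. The 24-hour albumin ANCOVA has no other post-baseline value. These losses would be related to renal function. The supplementary ITT analysis in SAP 2.5.4 keeps whatever was collected.

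Separately, the first sentence of Protocol 6.2.2 cites Table 6-3 (the permitted list) where Table 6-2 is meant. That is a clerical correction and adds no weight here.
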